Type 2 diabetes mellitus (T2DM) is a common metabolic disease that affects 21 million Americans and is associated with significant morbidity and mortality secondary to micro- and macrovascular complications. Subjects with T2DM manifest insulin resistance in skeletal muscle, liver and adipocytes and impaired insulin secretion. Although many therapeutic agents have been developed to target the pathogenic abnormalities in subjects with T2DM, the current ADA recommendation for pharmacological therapy in T2DM remains based on monotherapy, with dose escalation, followed by sequential addition of oral antidiabetic agents and eventually insulin to control blood glucose levels. Unfortunately, the majority of type 2 diabetic individuals in the US fail to achieve the recommended level of glycemic control ($\text{HbA}_{1c} < 6.0\%$) using this approach. In this study, I propose to explore the efficacy of a novel therapeutic approach to attain glycemic control in T2DM subjects. This novel approach is based upon the initiation of triple combination therapy at the time of diagnosis with agents that target specific pathogenic abnormalities present in T2DM. Two groups of newly diagnosed, drug naive T2DM subjects will be studied: (i) Group I will receive triple combination therapy with metformin, pioglitazone, and exenatide as initial therapy; (ii) Group II will be started on metformin monotherapy followed by sequential addition of a sulfonylurea and then glargin insulin. The goal of therapy in both groups is to reduce the $\text{HbA}_{1c} < 6.0\%$. Subjects will be recruited over one year and followed for 2 years (total study duration =3 years). The primary outcome will be the difference in HbA_{1c} between Groups I and II. Secondary outcomes will include failure to achieve the glycemic goal ($\text{HbA}_{1c} < 6.0\%$), improvements in insulin resistance, beta cell function, markers of inflammation, markers of oxidative stress, and carotid intima media thickness. I hypothesize that subjects started on combination therapy at the time of diagnosis of T2DM will have better and more durable glycemic control, a lower rate of therapeutic failure, enhanced insulin sensitivity, and improved/preservation of beta cell function compared to subjects receiving the “conventional” ADA-recommended stepped-therapeutic approach with “standard” medications. I also hypothesize that subjects started on initial combination therapy will have: (i) lower levels of inflammatory markers and (ii) reduced carotid IMT. On a long-term basis, one would expect the superior metabolic control in T2DM who receive aggressive combination therapy from onset to have a lower rate of diabetic complications.

The results of this study will provide a novel, more progressive therapeutic approach to the treatment of T2DM, based upon correction of known pathogenic abnormalities responsible for the disease.

Data Analysis and Statistical Methods

Values are presented as mean \pm SEM. Two-sided t test was used to compare mean differences between treatment arms, and the χ^2 test was used to test the significance of discrete variables. The Cox proportional hazards model was used to estimate the influence of therapy on failure to maintain the treatment goal. The model was adjusted for other confounders (namely, age, sex, BMI, disease duration, and baseline HbA1c level).

Sample size calculation:

The study was powered to detect a 0.5% (60.95 SD) HbA1c difference between the two treatment arms based on the HbA1c decrease in the PROactive study (22). We calculated that 76 patients who completed the study would be required in each arm to detect significant difference between the two groups at $\alpha = 0.05$. A detailed description of the sample size

calculation is given in the Supplementary Material.

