Official Study Title: Durability of Combination Therapy With
Exenatide/Pioglitazone/Metformin vs. Conventional Therapy in New Onset
T2DM

NCT number: NCT01107717

IRB Approval Date: 12.04.2019

Unique Protocol ID: HSC20080456H

[Click here for a complete set of instructions for this form.](#)

If an item does not apply to your research project, simply indicate that the question is "**not applicable**."

For the following Sections: 1. "Purpose and Objectives"; 3. "Study Design"; and 4. "Study Population," and 5 – 12, you may copy and paste the relevant passages from the sponsor's full protocol or grant application (only citing the page number and section **will not** be acceptable).

For Section 2, "Background" you may cite the relevant passages (page number and section) from the sponsor's full protocol or grant application.

Click once on the highlighted entry in each box to provide your response. Click the item number/letter for detailed instructions for that question. If your response requires inserting a table, picture, etc, you will need to first delete the box that surrounds the answer and then insert your table or other special document.

1. Purpose and objectives.

List your purpose and objectives:

We hypothesize that initiation of combination therapy at the time of initial diagnosis of type 2 diabetes with antihyperglycemic drugs (pioglitazone, metformin, and exenatide) that specifically target known pathogenic defects (insulin resistance and beta cell dysfunction) responsible for impaired glucose homeostasis will achieve superior and more durable glycemic control and more effectively reduce cardiovascular risk factors compared to the stepwise approach currently recommended by the American Diabetes Association (ADA) and European Association for the Study of Diabetes (EASD).

Specifically, We will test the effect of initiating therapy in newly diagnosed type 2 diabetic subjects with combination pioglitazone/metformin/exenatide therapy compared to the ADA recommended approach (start with metformin and add a second or third oral agent, and then proceed to insulin) on:

- 1) Achievement and maintenance of glycemic control (HbA_{1c} <6.5%)
- 2) Reduction in whole body (muscle) insulin resistance and improvement in beta cell function.
- 3) Improvement in cardiovascular risk factors
- 4) Decrease in carotid intima media thickness, a surrogate measure of atherosclerosis

2. Background.

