Two landmark studies, the DCCT (10) and the UKPDS (11), as well as others (12-15) unequivocally have documented that improved control of the plasma glucose concentration in T2DM subjects reduces the risk of both microvascular and macrovascular complications, demonstrating that chronic exposure of tissues to hyperglycemia triggers pathologic processes that lead to organ damage. A 1% decrease in $\text{HbA}_{1\text{C}}$ has been shown to cause an ~35% reduction in the incidence of microvascular complications (10,11,14) and maintaining the $\text{HbA}_{1\text{C}} < 6\%$ has been reported to completely prevent the development of retinopathy in T2DM subjects (13). Further, in the DCCT continuation study (EDIC), subjects who initially were treated aggressively with intensive insulin therapy and achieved a $\text{HbA}_{1\text{C}} < 7\%$ early in the course of their disease maintained a lower risk for microvascular complications many years later even though their $\text{HbA}_{1\text{C}}$ increased to 8% compared to subjects who initially were less controlled (16). This observation emphasizes the importance of achieving good glycemic control at the time of diagnosis and of maintaining the level of glycemic control in order to reduce the risk of microvascular complications. The UKPDS (11), DCCT (15), and Kumamoto [14] studies also have shown that improved glycemic control reduces the risk of atherosclerotic cardiovascular complications. The results of these studies have prompted the professional organizations of health care providers (American Diabetes Association [17], American College of Physicians [18], American Association for Clinical Endocrinology (AACE) [19], and the European Association for the Study of Diabetes [20]) to recommend glycemic goals as close to normal as possible while avoiding hypoglycemia. The ADA's target goal for $\text{HbA}_{1\text{C}}$ is $\leq 7.0\%$, while the AACE's and the EASD's goal is $\leq 6.5\%$.

ADA Recommendation for Therapy

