The ADA recommends that, at the time of diagnosis, subjects with type 2 diabetes be started on metformin, in addition to lifestyle intervention (17). Metformin is safe and effective, reducing $\text{HbA}_{1\text{C}}$ by ~1.5% (21). However, its efficacy wanes with time (22,23). Both the UKPDS (23) and ADOPT (22) studies have demonstrated that, despite a significant initial decrease in $\text{HbA}_{1\text{C}}$ following initiation of metformin therapy, beta cell function continues to deteriorate progressively, resulting in subsequent treatment failure. The current ADA (and EASD) recommendation is to add a sulfonylurea (less commonly a thiazolidinedione) or basal insulin in stepwise fashion upon therapeutic failure, i.e. increase in $\text{HbA}_{1\text{C}}$ to $> 7.0\%$ (17,20). Although this therapeutic approach will achieve adequate glycemic control in many T2DM subjects, diabetes is a progressive disease (22,23) and after 1-2 years the $\text{HbA}_{1\text{C}}$ rises to values $> 7.0\%$, requiring the addition of a second antidiabetic medication, usually a sulfonylurea. Moreover, this therapeutic approach is based upon reduction of the plasma glucose concentration rather than on correction of the underlying defects which cause the hyperglycemia (beta cell failure and insulin resistance). Most importantly, we (24) and others (25) have shown that at the stage of impaired glucose tolerance (i.e., upper tertile of 2-hour plasma glucose during OGTT = 180-199 mg/dl) approximately 75-80% of beta cell function has been lost (24-26). Thus, if therapy is initiated with drugs, i.e., metformin or sulfonylureas that do not halt the progressive beta cell failure (22,23,27), eventually there will be a complete loss of beta cell function, rendering the diabetic patient dependent on insulin therapy for glycemic control (28). In most studies (28-30) insulin therapy is associated

with significant weight gain and an increased rate of hypoglycemia, which presents a major obstacle in achieving the desired level of glycemic control (28-30).

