No previous study has evaluated the efficacy and durability of combined pharmacological therapy at the time of diagnosis of diabetes with drugs that preserve beta cell function. Furthermore, no previous study has achieved the recommended goal of glycemic control (HbA_{1c} <6.5%) as its primary outcome. In this study we will initiate therapy in subjects with type 2 diabetes at the time of diagnosis with triple therapy (pioglitazone, metformin, exenatide). Pioglitazone and exenatide both exert effects to preserve beta cell function, while pioglitazone, and metformin to a lesser extent, are excellent sensitizers. All three drugs effectively reduce the HbA_{1c} and have beneficial cardiovascular actions. The primary outcome variable is the achievement and maintenance of the recommended target for glycemic control (HbA_{1c} <6.5%) in subjects with type 2 diabetes. We will compare the efficacy of two therapeutic regimens: (i) triple therapy (pioglitazone, metformin, exenatide) at the time of diagnosis of T2DM versus (ii) stepwise therapy starting with metformin and subsequent addition of sulfonylurea and basal insulin (i.e., the "standard" approach) in achieving this goal. The first intervention is based on the novel concept of initiating therapy at the time of diagnosis with combination therapy using agents that correct specific pathophysiologic defects that are characteristic of T2DM (insulin resistance and beta cell failure). The second intervention is based upon stepwise addition of antidiabetic agents to reduce the HbA_{1c} according to the current ADA therapeutic recommendation.

3. Study Design.

Describe the study design (e.g., single/double blind, parallel, crossover, etc.) Consider inserting a scheme to visually present the study design.

Research Design and Methods

Subjects:

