If, at any time after achieving a HbA_{1C} $\leq 6.0\%$, the HbA_{1C} rises above 6.0% and the subject is on submaximal doses of metformin or pioglitazone or exenatide, the medication(s) will be titrated up to the maximally effective dose and the subject will not be considered a treatment failure.

If, after month six, the HbA_{1C} $\geq 6.0\%$ and the subject is on maximum doses of all triple therapy medications, the subject will be considered a treatment failure. If, after month 6, the HbA_{1C} rises to $> 6.5\%$, bedtime glargine insulin (10-20 units) will be started and titrated to a maximum of 60 units to achieve a FPG < 110 mg/dl and HbA_{1C} $< 6.0\%$. If more than 60 units of glargine insulin is required to reduce the HbA_{1C} $< 6.5\%$, regular insulin will be added to each meal and adjusted based upon the pre- and post-meal blood glucose levels. These "treatment failure" subjects will continue with all follow up visits/procedures. Throughout the titration process, downward adjustments will be allowed for the development of hypoglycemia, as defined by a blood glucose less than 60 mg/dl with (symptomatic hypoglycemia) or without (asymptomatic hypoglycemia) symptoms. Serious hypoglycemia is defined as any hypoglycemic reaction requiring assistance from a third party for recovery.

GROUP II: Group II will be started on metformin, 1000 mg with breakfast and 1000 mg with supper.

If, after month one, the FPG ≥ 110 mg/dl or HbA_{1C} $\geq 6.0\%$, glipizide (5 mg) will be added: 1-2 tablets with breakfast depending on the FPG, HbA_{1C}, and discretion of the investigator in order to avoid hypoglycemia.

If, after month two, the FPG ≥ 110 mg/dl or HbA_{1C} $\geq 6.0\%$, the glipizide dose will be increased to 4 tablets (20 mg/dl).

If, after month three, the FPG > 110 mg/dl or HbA_{1C} $> 6.0\%$, bedtime basal insulin (10-20 units) will be started and titrated up to achieve a FPG < 110 mg/dl or HbA_{1C} $< 6.0\%$

If, at any time after achieving a HbA_{1C} $< 6.0\%$, the HbA_{1C} rises above 6.0% and the subject is on submaximal doses of metformin or glipizide or glargine insulin, the medication(s) can be titrated up to the maximally effective dose and the subject will not be considered a treatment failure.

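### Group II is labelled the ADA-recommended approach but escalates at HbA1c 6.0%, not above 7.0%, so effect sizes and secondary-endpoint differences should not be read as effects versus ADA care

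*Combined protocol and SAP*

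**What the plan says.** **The label.** Section 1 (Purpose and objectives) tests initial triple therapy "compared to the ADA recommended approach (start with metformin and add a second or third oral agent, and then proceed to insulin"; it gives no HbA1c trigger. The last paragraph of Section 2 says the second regimen adds drugs stepwise "according to the current ADA therapeutic recommendation". The Abstract also calls the control strategy ADA-recommended.

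**The ADA approach as the protocol describes it.** Section 2, under ADA Recommendation for Therapy, says a sulfonylurea (less often a thiazolidinedione) or basal insulin is added "upon therapeutic failure, i.e. increase in $\text{HbA}_{1\text{C}}$ to $> 7.0\%$ (17,20"), and that HbA1c passes that level after 1-2 years. Earlier parts of Section 2 give the ADA goal as 7.0% or below.

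**Group II as run.** In Section 6a, after month one "glipizide (5 mg) will be added" if FPG is 110 mg/dl or more or HbA1c is 6.0% or more. The dose rises after month two on the same trigger. Basal insulin starts after month three if FPG is above 110 mg/dl or HbA1c is above 6.0%. Section 4 requires HbA1c above 6.5% at entry.

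**The target.** Section 3 and the Abstract give both groups a goal below 6.0%. The Abstract says most US patients "fail to achieve the recommended level of glycemic control" and puts that level at below 6.0%. The end of Section 2 puts the recommended goal at below 6.5%.

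**A further conflict.** Section 8 says that it is Group I that will be treated according to ADA recommendations.

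**The concern.** A reader of the objectives or the Abstract would take Group II to be ADA care. By the protocol's own account it is the ADA drug sequence run on a lower trigger and a faster timetable. Two inferences are then at risk.

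- **Size of the HbA1c effect.** The difference estimated is against a control arm pushed below 6.0%. It does not estimate the difference against add-on above 7.0%.
- **Secondary endpoints.** Section 6a lists hypoglycaemia, body weight, beta cell function, insulin resistance and carotid intima media thickness; Section 1 adds cardiovascular risk factors. Earlier sulfonylurea and insulin could raise hypoglycaemia and weight in Group II, which favours Group I, and could move the others either way. Section 6c lists hypoglycaemia and weight gain as likely with the Group II drugs (more than 20 in 100), although weight gain is also listed as likely with pioglitazone in Group I.

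Treatment failure in Section 6a is also tied to 6.0%. It therefore does not measure failure of the ADA approach as Section 2 describes it.

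**Working it through.** **1. The passages side by side.**

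| Feature | ADA approach as described (Section 2) | Group II (Section 6a) |
|---|---|---|
| Goal | HbA1c 7.0% or below | HbA1c below 6.0% |
| First add-on trigger | HbA1c above 7.0% | HbA1c 6.0% or more, or FPG 110 mg/dl or more |
| Timing of first add-on | on failure, after 1-2 years | after month one |
| Basal insulin | an add-on option on failure (above 7.0%) | after month three, HbA1c above 6.0% or FPG above 110 mg/dl |

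The drug order agrees with Section 2. It agrees less well with Section 1, which speaks of a second or third oral agent before insulin. The triggers, timing and goal do not agree. Someone entering on metformin with HbA1c between 6.5% and 7.0% is below the Section 2 trigger and above the Group II trigger.

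**2. The two arms.** Both are titrated at 6.0% from month one. Insulin entry differs: Group II after month three at HbA1c above 6.0% or FPG above 110 mg/dl, Group I after month six at HbA1c above 6.5%.

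**3. The plan's own sample size.** Inputs from the statistical section: difference 0.5, SD 0.95 (the printed 60.95 read as plus-minus 0.95), two-sided alpha 0.05. Power is not stated; 90% is inferred because it returns the stated figure.

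n per arm = 2 × (1.960 + 1.282)² × 0.95² / 0.5² = 2 × 10.51 × 0.9025 / 0.25 = 75.9, rounded up to 76, as stated. At 80% power the result would be 57.

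**4. Direction on HbA1c.** If earlier escalation lowers Group II's HbA1c, the true difference shrinks. The documents do not say by how much, so these differences are assumptions (SD 0.95):

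| True difference | Power, 76 per arm | Power, 300 per arm |
|---|---|---|
| 0.5 | 90% | above 99.9% |
| 0.4 | 74% | 99.9% |
| 0.3 | 50% | 97% |
| 0.2 | 25% | 73% |

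The 300 is half of the 600 completers in Section 4. If a trigger above 7.0% had instead widened the difference to 0.7, power at 76 per arm would be 99.5%. The mismatch therefore costs power and does not create a spurious advantage for Group I.

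**5. Illustrative share between the triggers.** Assume on-metformin HbA1c is normal with SD 0.95, and that 720 are split equally (360 per arm). The share is Φ((7.0 − mean)/0.95) − Φ((6.0 − mean)/0.95).

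- Mean 6.5: Φ(0.526) − Φ(−0.526) = 0.40, about 144 people
- Mean 7.0: Φ(0) − Φ(−1.053) = 0.35, about 127
- Mean 7.5: Φ(−0.526) − Φ(−1.579) = 0.24, about 87

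The means are assumed, and the SD is borrowed from the sample-size statement. The FPG trigger and down-titration are ignored.

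**The case against.** The strongest reply is that the trial compares initial combination with sequential addition, and that a shared target isolates this. Running the control to 7.0% and the intervention to 6.0% would confound strategy with target. This stands, and it is why the randomised comparison is sound.

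A reader might infer that the trial cannot support any claim of superiority over ADA care. The documents do not support that. A control arm escalated earlier should have lower HbA1c, so an HbA1c advantage over it would, if anything, also hold against a less intensive strategy. This assumes that earlier escalation does not raise HbA1c, for instance through down-titration after hypoglycaemia. The argument is confined to HbA1c and does not carry over to the secondary endpoints.

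It can also be said that Section 1 defines the ADA approach by drug order alone, that the primary endpoint calls Group II simply stepwise therapy, and that Section 2 reports the professional bodies as wanting to "recommend glycemic goals as close to normal as possible while avoiding hypoglycemia". The neutral label is helpful where it appears. The general aim does not remove the conflict, because the same paragraph then gives 7.0% or below as the ADA target and the next subsection gives an explicit trigger above 7.0%.

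Finally, no objective or hypothesis claims a hypoglycaemia or weight benefit over ADA care, and Section 6a allows discretion and down-titration to limit hypoglycaemia. That is fair: the misattribution is a risk created by the label, not a claim that the plan makes.

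**Conclusion.** The comparator is wrongly described. By the protocol's own account of ADA practice, Group II is a more intensive version of it: the HbA1c trigger is one percentage point lower (6.0% against 7.0%), an FPG trigger is added, and the first add-on comes after one month instead of 1-2 years.

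Superiority on HbA1c is not undermined, on the assumption that earlier escalation does not raise HbA1c. The effect size cannot be read as the effect versus ADA practice. Differences in hypoglycaemia, weight and the metabolic and vascular endpoints should not be attributed to ADA-recommended care. The documents do not allow the size of these distortions to be estimated. The 24% to 40% range shows only that the group between the two triggers could be substantial.

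**What to change.** Reconcile Section 1, Section 2 (the ADA subsection and the closing paragraph), the Group II algorithm in Section 6a, Section 8 and the Abstract. No view is taken here on which threshold is clinically right.

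If the Group II algorithm stands:

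- Name the comparator throughout as stepwise metformin, sulfonylurea and basal insulin titrated to HbA1c below 6.0%.
- Limit conclusions to initial combination versus sequential therapy at that common target, and say so explicitly for hypoglycaemia, weight, beta cell function, insulin resistance, cardiovascular risk factors, carotid thickness and treatment failure.
- Reconcile the recommended level in the Abstract with the goals given in Section 2.
- Resolve the statement in Section 8 that Group I follows the ADA recommendations.

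The cost is wording and a slightly narrower claim. No sample-size change is needed.
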